1.0 Objectives

This is a pilot study to explore the feasibility of using optical models to predict how multifocal contact lens designs affect retinal defocus and visual performance. Multifocal contact lens designs are being used and optimized for myopia control. However, these lens designs must be tested on-eye to measure their effect on retinal defocus and visual performance. This process is expensive and time consuming. The purpose of this study is to develop a model to predict changes in retinal defocus and visual performance with multifocal soft contact lenses.

We hypothesize that optical modelling can be used to accurately predict changes in retinal defocus and visual performance with multifocal soft contact lenses. This hypothesis is based on published works that show optical models can replicate central and peripheral wave aberrations (Polans et al. 2015, Nadeem Akram et al. 2018) and that some visual quality metrics can predict changes in visual performance due to the optical aberrations. (Ravikumar et al. 2013)

The study will also identify visual quality metrics that are correlated with changes in visual performance with different multifocal contact lens designs, and how some optical properties of the eye change with multifocal contact lenses.

2.0 Background

Most multifocal contact lenses being studied for myopia control such as the Biofinity Multifocal D, (Walline et al. 2020) Proclear Multifocal D (Walline et al. 2013) and NaturalVue multifocal lenses (Cooper et al. 2018) were initially designed for presbyopia. Based on results from animal studies, (Smith 2011) it is hypothesized that these lenses are able to slow myopia progression by simultaneously providing clear foveal vision and myopic defocus. Thus, the initial steps in assessing the efficacy of any new myopia control lens must include an assessment of its effect on both visual performance and retinal defocus. Currently, this assessment is done on-eye in a cohort study. This process is expensive, time consuming and inefficient, and can severely hamper the ability to test several new multifocal contact lens designs.

The rationale for this study is to create a model that can predict changes in retinal defocus and visual performance with novel lens designs. With this model, several multifocal contact lens designs can be tested, and only promising lens designs are manufactured for further on-eye testing. This model can then be used by us and other researchers to quickly test the performance of several lens designs. Lens designs that maintain good visual performance with a maximum myopic change in retinal defocus have a high potential of being a good myopia control lens that warrant on-eye testing in a cohort study.

3.0 Inclusion and Exclusion Criteria

Inclusion Criteria

FULL PROTOCOL TITLE: Evaluating Contact Lens Optics

- Able to read and understand the informed consent document
- 18 to 39 years of age (inclusive)
- Best corrected visual acuity of 20/25 or better in the right eye
- Refractive error from -1.00D to -6.00D with astigmatism less than or equal to -1.00D in the right eye (corneal plane).

Exclusion Criteria

- Any ocular or systemic conditions affecting vision, refraction, or the ability to wear a soft contact lens.
- History of ocular trauma or surgery causing abnormal or distorted vision
- Current Rigid Gas Permeable (RGP) contact lens wearers
- Unwilling to have contact lens fit photographed
- Pregnant and/or lactating females, by self-report

A screening examination will be performed on all potential subjects to determine their eligibility for the study. Eligibility will be based on the listed criteria and will be determined by the study personnel listed on the study protocol.

The following special populations will be excluded from the study;

- Adults unable to consent
- Individuals who are not yet adults (infants, children, teenagers less than 18 years old)
- Pregnant women, by self report*
- Prisoners⁺

* Pregnant and/or lactating women will be excluded from the study because of the potential for shifts in the refractive components of the eyes during pregnancy, which would affect the study results. In clinical practice, pregnant or lactating women typically do not have dilation drops instilled when not necessary, unless as part of a comprehensive eye examination, to avoid any potential side effects for the child.

⁺ Prisoners will be excluded from the study because the study requires the participant to be able to come to the University of Houston College of Optometry due to the specialized instruments needed to complete the study visit.

The following special populations may be included in the study;

- Students for whom the Principal Investigator have direct access to/influence on grades

FULL PROTOCOL TITLE: Evaluating Contact Lens Optics

4.0 Vulnerable Populations

Study subjects may be students for whom the principal investigator has access to or influence over their grades. For this reason, the principal investigator will not be responsible for recruiting or obtaining consent from students in their own courses in order to prevent undue influence or coercion. A study team member (e.g., sub-investigator) without access to or influence on grades will be responsible for these tasks.

5.0 Number of Subjects

The proposed study is a single site study and will be conducted at the University of Houston College of Optometry. To ensure that at least 10 subjects complete the study, up to 25 subjects will be enrolled and screened for inclusion in the study.

For this study, a sample size of 10 gives the study 80% power at an alpha level of 0.05 to detect whether a correlation of at least 0.8 exists between change in peripheral refraction with a multifocal contact lens compared to the change predicted by the model.

This study will not present more than minimal risk to the subjects. All visits will involve procedures and instruments that are routinely used in optometric examinations. The contact lenses the subjects will wear are FDA approved.

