8.0 Study Endpoints

FULL PROTOCOL TITLE: Evaluating Contact Lens Optics

This is a minimal risk study. Correlations between measured changes in peripheral refraction and visual performance will be compared to modelled changes in these outcomes.

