9.0 Procedures Involved

The study is a single visit, non-dispensing study of changes in visual performance and retinal defocus with multifocal contact lenses. The targeted number of participants is at least 10. Eligibility for the study will be determined during a screening examination after informed consent has been obtained. The study visit is expected to last approximately 2.5 hours and only approved clinical instruments will be used for examinations. Two FDA-approved soft contact lenses will be used in the study; a single vision contact lens and a multifocal contact lens.

Study Procedures

Item	Details
Informed Consent	Review and complete the informed consent form
Subject Eligibility	Review inclusion and exclusion criteria
Auto-refraction	Subject's refractive error and corneal curvature will be measured using a clinical, non-contact autorefractor.
Subjective Refraction	A subjective measurement of the subject's refractive error (i.e., prescription) will be determined using a phoropter.
Slit Lamp Examination	A slit lamp (i.e., a microscope used to examine the eye) will be used to assess the health of the subject's eyes. Standard clinical dyes (sodium fluorescein) will be used to assess the health of the front surface of the eye.
Pupil dilation and cycloplegia	After instillation of a topical anesthetic (either 0.5% proparacaine or 0.5% tetracaine), the pupil of each subject's right eye will be pharmacologically dilated using either 1% tropicamide alone or in combination with 2.5% phenylephrine to ensure adequate pupil dilation.
Optical biometry	A non-contact optical biometer will be used to measure the biometrics of the eye including axial length, anterior chamber depth, lens thickness and vitreous chamber depth.
Aberrometry	Eye aberrations will be measured using a standard clinical instrument with and without wearing FDA-approved contact lenses.
Corneal topography	The surface curvature and elevation of the cornea with and without FDA-approved contact lenses will be measured using a corneal topographer.

FULL PROTOCOL TITLE: Evaluating Contact Lens Optics

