20.0 Data Management

Data will be stored both in a paper file and electronically. Paper files will be locked in the research lab, and electronic data will be stored on a password protected computer. Data will be kept for a minimum of 3 years after completion of the project.

Data analyses will be conducted using standard software packages. Descriptive statistics will be conducted to describe the data. Tests of normality will then be conducted followed by appropriate parametric or non-parametric hypothesis testing and correlation analyses.

FULL PROTOCOL TITLE: Evaluating Contact Lens Optics

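### The hypothesis is accurate prediction, but the only named measure of measured against modelled change is a correlation, which cannot detect a constant or scale error

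*Combined protocol and SAP*

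**What the plan says.** Section 1.0 states the hypothesis: "We hypothesize that optical modelling can be used to accurately predict changes in retinal defocus and visual performance with multifocal soft contact lenses". It adds a separate exploratory aim, to "identify visual quality metrics that are correlated with changes in visual performance with different multifocal contact lens designs".

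Section 2.0 gives the intended use. With the model, "several multifocal contact lens designs can be tested, and only promising lens designs are manufactured for further on-eye testing". The designs to be favoured are "Lens designs that maintain good visual performance with a maximum myopic change in retinal defocus".

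Section 5.0 justifies ten completers by 80% power at an alpha of 0.05 for a "correlation of at least 0.8 exists between change in peripheral refraction with a multifocal contact lens compared to the change predicted by the model". It states neither the null value nor whether the test is two-sided.

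Section 8.0 describes the endpoints in one sentence: "Correlations between measured changes in peripheral refraction and visual performance will be compared to modelled changes in these outcomes". Section 20.0 plans descriptive statistics, and then: "Tests of normality will then be conducted followed by appropriate parametric or non-parametric hypothesis testing and correlation analyses".

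Section 9.0 limits the lenses: "Two FDA-approved soft contact lenses will be used in the study; a single vision contact lens and a multifocal contact lens".

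No section names a mean error, limits of agreement, a concordance coefficient, a calibration slope or an acceptable error in dioptres.

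**The concern.** Accuracy means that the predicted change is close to the measured change in dioptres. A correlation asks only whether eyes with larger predicted changes tend to have larger measured changes. Adding a constant to every prediction, or multiplying all of them by a positive factor, leaves the correlation exactly as it was.

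The single multifocal lens sharpens the problem. If each subject contributes one value, which the sample size of ten suggests but the protocol does not state, the correlation reflects only differences between eyes. The average effect of the lens drops out of it. That average is what a model for screening lens designs most needs to get right.

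What is at stake is evidence on whether the predicted size of the change can be trusted. The mismatch concerns the accuracy hypothesis, mainly for peripheral refraction. For the visual-quality-metric aim, correlation is a suitable measure.

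**Working it through.** **Inputs.** From Section 5.0: n = 10, correlation 0.8, power 80%, alpha 0.05. Assumed: two-sided test, null correlation 0, one value per subject, bivariate normal data. The documents give no SD for the change in peripheral refraction, so errors are expressed in between-eye SDs of measured change, and then in dioptres over an assumed range.

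**1. The plan's own figure.** With Fisher's z, atanh(0.8) = 1.0986, and

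n = ((1.960 + 0.842) / 1.0986)² + 3 = 9.50, rounded up to 10.

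Power at n = 10 is Φ(√7 × 1.0986 − 1.960) = Φ(0.947) = 82.8%. Simulating the t-test of r (200,000 replicates) gives 86.9%. The plan's figure is reproduced.

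**2. What the test sees under model error.** Let the model output be k × prediction + b, with unit SDs and ρ = 0.8. Here k rescales the predictions about their mean and b is the mean error.

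- Lin concordance = 2ρk / (1 + k² + b²)
- Root mean square error (RMSE) = √(1 + k² − 2ρk + b²)

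| Model error | k | b | Power of correlation test | Concordance | RMSE (SDs) |
|---|---|---|---|---|---|
| None | 1 | 0 | 86.9% | 0.80 | 0.63 |
| Constant, 1 SD | 1 | 1 | 86.9% | 0.53 | 1.18 |
| Constant, 2 SD | 1 | 2 | 86.9% | 0.27 | 2.10 |
| Scale halved | 0.5 | 0 | 86.9% | 0.64 | 0.67 |
| Scale doubled | 2 | 0 | 86.9% | 0.64 | 1.34 |
| Halved, plus 1 SD | 0.5 | 1 | 86.9% | 0.36 | 1.20 |

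**3. In dioptres.** For a 0.5 D error in every eye and assumed between-eye SDs of 0.25, 0.5 and 1.0 D, b is 2, 1 and 0.5. The correlation stays at 0.8; concordance is 0.27, 0.53 and 0.71.

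**4. What a just-significant result shows.** The critical value at n = 10 is r = 2.306 / √(8 + 2.306²) = 0.632. The Fisher 95% confidence interval there is 0.004 to 0.902. With equal SDs and no bias at all, the limits of agreement are ±1.96 × √(2 × (1 − 0.632)) = ±1.68 between-eye SDs.

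**5. What the same ten pairs could show.** At ρ = 0.8 with equal SDs, the SD of the differences is √(2 × 0.2) = 0.632 between-eye SDs. Constant errors of 1 and 2 between-eye SDs are then 1.58 and 3.16 SDs of the differences. A paired t-test detects them with 99.3% and over 99.9% power. For a 0.5 D error at the three assumed SDs, power is over 99.9%, 99.3% and 61%.

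The 95% interval half-widths, in SDs of the differences, are:

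- mean difference: 2.262 / √10 = 0.72
- each limit of agreement: 2.262 × √(1/10 + 1.96²/18) = 1.27

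For the calibration slope (measured regressed on modelled), the simulated median half-width at ρ = 0.8 is about 57% of the slope: 0.573 at a true slope of 1.0 and 0.458 at 0.8. For an otherwise calibrated model, the interval excludes 1 in 87% of replicates if predictions are doubled (slope 0.5), but in only 41% if they are halved (slope 2.0).

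**The case against.** The strongest reply is that this is a pilot for developing a model. A constant or linear scale error can be removed by recalibration, whereas weak association cannot, so correlation is a reasonable first measure of feasibility. A uniform error also leaves the ranking of designs unchanged, and on-eye testing would follow. All of this is fair, and it limits the severity. But the protocol states an accuracy hypothesis, and recalibration needs the bias and slope that the plan does not ask for.

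Other points stand in part:

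- Because changes are compared, offsets common to the lens and reference conditions cancel. Only an error specific to the lens effect survives. The error sizes used here are illustrations; nothing in the documents suggests a likely value.
- The protocol sets no success criterion. That a significant correlation would be read as support is an inference from the power statement.
- Section 20.0 leaves room for a paired comparison of measured and modelled change, but neither names one nor ties a test to that comparison. A non-significant paired test with ten subjects would not demonstrate accuracy in any case.
- If several retinal locations per eye are pooled, the power and precision figures no longer apply. The invariance of the correlation still does.
- The concordance table takes equal SDs as its starting point, where the calibration slope is 0.8. Starting instead from a slope of 1 (prediction SD 0.8), concordance is 1.28/1.64 = 0.78 with no error, 0.64/1.16 = 0.55 halved and 2.56/3.56 = 0.72 doubled. The conclusion is the same.

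**Conclusion.** The concern holds. The sample size is correct for testing a correlation against zero, but that test does not address accuracy. Under the assumptions of one value per subject, normal data and a true correlation of 0.8, its power is about 87% whether the model is unbiased, wrong by one or two between-eye SDs, or on half or double the right scale. Concordance over those cases ranges from 0.80 down to 0.27. That the correlation cannot see these errors is a mathematical fact and needs no assumption about SDs; only the dioptre illustrations do.

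This should be fixed, but it does not undermine the conduct of the study. The planned data can answer the accuracy question; the analysis text does not ask it.

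**What to change.** In Section 8.0, make agreement between measured and modelled change in peripheral refraction the primary measure. Report the mean difference with its 95% confidence interval and the 95% limits of agreement, both in dioptres, and the calibration slope with its 95% interval. The sponsor should state the acceptable error in dioptres before the data are analysed. Report the same for visual performance where the model output is in the same units. Keep the correlation, with its interval, as supportive and as the measure for the visual-quality-metric aim.

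In Section 5.0, state the unit of analysis. Say that ten completers give about 83% power (Fisher z, two-sided 5%) to reject a zero correlation if the true value is 0.8. Add the expected precision with one value per subject: half-widths of about 0.72 SD of the paired differences for the mean difference, 1.27 SD for each limit of agreement, and 57% of the slope's value at a true correlation of 0.8. Limit any conclusion on accuracy to the one multifocal lens tested.

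The cost is text only, with no extra subjects or procedures. The claim becomes harder to meet, and estimates from ten subjects will be imprecise. The slope is the weakest of them and should be reported as an estimate, not used as a pass/fail test.

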6.0 Recruitment Methods

Potential subjects will be recruited from the faculty, patients, students and staff (including relatives) of the University Eye Institute/University of Houston College of Optometry, as well as the surrounding community via word of mouth, print media (e.g., study fliers, newspaper adverts), telephone and electronic media (e.g., email, College of Optometry and The Ocular Surface Institute Websites, social media).

7.0 Study Timelines

The study is a single visit study. Subjects will be invited to participate in a study visit that will last approximately 2.5 hours. We expect to take up to 9 months to complete all visits and an additional 3 months to complete primary analyses after the last subject completes the study.

8.0 Study Endpoints

FULL PROTOCOL TITLE: Evaluating Contact Lens Optics

This is a minimal risk study. Correlations between measured changes in peripheral refraction and visual performance will be compared to modelled changes in these outcomes.

9.0 Procedures Involved

The study is a single visit, non-dispensing study of changes in visual performance and retinal defocus with multifocal contact lenses. The targeted number of participants is at least 10. Eligibility for the study will be determined during a screening examination after informed consent has been obtained. The study visit is expected to last approximately 2.5 hours and only approved clinical instruments will be used for examinations. Two FDA-approved soft contact lenses will be used in the study; a single vision contact lens and a multifocal contact lens.

Study Procedures

Item	Details
Informed Consent	Review and complete the informed consent form
Subject Eligibility	Review inclusion and exclusion criteria
Auto-refraction	Subject's refractive error and corneal curvature will be measured using a clinical, non-contact autorefractor.
Subjective Refraction	A subjective measurement of the subject's refractive error (i.e., prescription) will be determined using a phoropter.
Slit Lamp Examination	A slit lamp (i.e., a microscope used to examine the eye) will be used to assess the health of the subject's eyes. Standard clinical dyes (sodium fluorescein) will be used to assess the health of the front surface of the eye.
Pupil dilation and cycloplegia	After instillation of a topical anesthetic (either 0.5% proparacaine or 0.5% tetracaine), the pupil of each subject's right eye will be pharmacologically dilated using either 1% tropicamide alone or in combination with 2.5% phenylephrine to ensure adequate pupil dilation.
Optical biometry	A non-contact optical biometer will be used to measure the biometrics of the eye including axial length, anterior chamber depth, lens thickness and vitreous chamber depth.
Aberrometry	Eye aberrations will be measured using a standard clinical instrument with and without wearing FDA-approved contact lenses.
Corneal topography	The surface curvature and elevation of the cornea with and without FDA-approved contact lenses will be measured using a corneal topographer.

FULL PROTOCOL TITLE: Evaluating Contact Lens Optics

Contact Lens Fitting	FDA-approved contact lenses will be fitted to the right eye. This includes checking the fit of the lenses (movement and centration), determining the appropriate lens power, and measuring visual acuity with the lenses. A picture of the contact lens fit will be taken to determine centration. Contact lenses will be fitted in random order based on a randomization schedule. Each subject will be fitted with a new contact lens. Contact lenses will not be reused between subjects.
Visual Acuity	High- and Low-Contrast Visual Acuity will be measured at various distances. Acuity measurements will be made with and without a standard optical setup to maintain a consistent artificial pupil size for all subjects.
Contrast Sensitivity	The subject's contrast sensitivity function will be measured by viewing a series of targets using an automated contrast sensitivity measuring device. Testing will be done through a standard optical setup to maintain a consistent pupil size for all subjects.
Intraocular Pressure	The intraocular pressure of the eye will be measured using a standard clinical instrument and either 0.5% proparacaine or 0.5% tetracaine.

Interested subjects will first go through an initial screening using a screening script before being scheduled. Potential subjects who pass the initial screening script will be scheduled and will initially complete the informed consent process. Should they agree to partake in the study, they will then undergo a screening examination to determine their eligibility for the study. As part of this examination, a standard manifest refraction will be performed to determine refractive error and best-corrected visual acuity.

Eligible subjects will be fitted with two different contact lenses (one sphere and one multifocal, in random order) in their right eye. Each subject will be fitted with a new, previously unworn contact lens. Next, the pupil of the right eye of the subject will be pharmacologically dilated. As the subjects are waiting for their pupil to be fully dilated, the axial length and other biometrics of the eye will be measured. After pupil dilation, the central and peripheral aberrations of the right eye of each subject will be measured.

Lens centration, corneal topography, central and peripheral aberrations, low- and high-contrast visual acuity, and contrast sensitivity will be measured with the first contact lens. After this, the second contact lens will be inserted, and the same measurements will be repeated.

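### Section 1.0 sets an aim across different multifocal designs, but the study uses one multifocal lens type, so that aim cannot be answered and a high correlation would not show that the model predicts a design's effect

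*Combined protocol and SAP*

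**What the plan says.** Section 1.0 (Objectives) presents a pilot to explore the "feasibility of using optical models to predict how multifocal contact lens designs affect retinal defocus and visual performance". It adds, as something this study will do, the aim to "identify visual quality metrics that are correlated with changes in visual performance with different multifocal contact lens designs". Section 2.0 (Background) gives the rationale as being to "create a model that can predict changes in retinal defocus and visual performance with novel lens designs".

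Section 9.0 (Procedures Involved) fixes the lenses: "Two FDA-approved soft contact lenses will be used in the study; a single vision contact lens and a multifocal contact lens". Further on it repeats: "Eligible subjects will be fitted with two different contact lenses (one sphere and one multifocal, in random order) in their right eye". The rest of that section describes a first and a second lens and no third. Power is chosen for each subject at fitting. No variation in add, zone layout or product is described.

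Section 5.0 bases the sample size on a correlation of at least 0.8 between the measured change in peripheral refraction with a multifocal lens, in the singular, and the change predicted by the model. Section 8.0 states the endpoint: "Correlations between measured changes in peripheral refraction and visual performance will be compared to modelled changes in these outcomes". Section 20.0 adds descriptive statistics, normality tests, unspecified hypothesis tests and correlation analyses. No section states an analysis of measured minus predicted change.

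**The concern.** An aim about several multifocal designs needs at least two of them. With one, multifocal design is a constant, and nothing in the data can show which metrics track performance as the design changes.

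The powered analysis makes this easy to miss. A correlation across eyes that all wear the same lens type asks whether the model orders those eyes correctly. It does not ask whether the model gets the average effect of the lens right, and that average effect is what a design is meant to change. If the objective stays as worded, a high r could be reported as having met an aim on which the study holds no information.

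**Working it through.** **Inputs from the documents.** Lens types: 2, of which 1 is multifocal (Section 9.0). N = 10, power 80%, alpha 0.05, correlation 0.8 (Section 5.0; sidedness not stated). The documents give no standard deviations or design effects.

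**1. The plan's own figure.** Fisher z test of zero correlation, two-sided:

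n = ((1.960 + 0.842) / atanh(0.8))² + 3 = (2.802 / 1.0986)² + 3 = 9.50, rounded up to 10.

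This matches the stated 10. At n = 10 the power is Φ(1.0986 × √7 − 1.960) = Φ(0.947) = 82.8%, and a simulation of the t-test for r gives 86.9%. The sample size is sound for what it tests. It reproduces with one value per subject, which supports reading the powered test that way.

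**2. Contrasts between multifocal designs.** Number of multifocal designs minus one = 1 − 1 = 0. The aim in Section 1.0 needs at least 1.

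**3. What the correlation can see.** Write the measured change in eye i as M_i = D + u_i, where D is the mean effect of the one multifocal lens. Write the prediction as P_i = bD + e_i, where b is how the model scales that effect (1 correct, 0 ignored, −1 reversed). D and bD are the same for every eye, and adding a constant leaves a correlation unchanged:

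corr(M, P) = corr(u, e), whatever the value of b.

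**4. Illustration.** Assumed settings: 10 subjects, corr(u, e) = 0.8, u and e each with SD 1, and D = 1 on that scale. There were 20,000 runs per row, with two-sided significance at |r| > 0.632.

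| Model's mean effect | Mean r | Runs significant |
|---|---|---|
| Correct (b = 1) | 0.78 | 87% |
| Ignored (b = 0) | 0.78 | 87% |
| Reversed (b = −1) | 0.78 | 87% |

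**5. What an agreement analysis would see.** Under the same assumptions, M_i − P_i has mean (1 − b)D and SD √(1 + 1 − 2 × 0.8) = √0.4 = 0.632. The standard error of the mean over 10 eyes is 0.632 / √10 = 0.200. The mean difference is therefore 0, 1 or 2 for b = 1, 0 or −1, that is 0, 5 or 10 standard errors from zero. The same data separate three models that the correlation cannot tell apart. They do so for this one lens only: with a single D, agreement here says nothing about another design.

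**The case against.** The strongest case on the other side has four parts.

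- **It is a pilot, and Section 2.0 is long-term rationale.** This stands in part. A reader might infer from Section 2.0 that this trial undertakes to test or screen novel designs. The text does not say so: it describes what a finished model would be used for, with on-eye testing still to follow. Starting with one multifocal lens is a defensible choice. But the aim about different multifocal designs is in Section 1.0 and is worded as something this study will do, so the pilot label does not rescue it.
- **The data do contain lens contrasts.** This stands. A reader might infer that the study says nothing at all about lens design. That is too strong: aberrations are measured with and without lenses, and single vision against multifocal is one genuine contrast. What is absent is any contrast between multifocals.
- **The unit of analysis is not defined.** This stands as a limit. Sections 5.0, 8.0 and 20.0 do not rule out pooling retinal locations within a subject, in which case the lens's defocus profile across the retina could enter the correlation. A constant error over all values would still drop out, and there would still be one multifocal design.
- **The lenses are not identical.** Power is fitted to each subject, over an eligible range of −1.00 D to −6.00 D. That is true, but power matched to refraction is not variation in multifocal design.

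Section 9.0 also speaks once of multifocal lenses in the plural. Its explicit count of two lenses, one of them single vision, settles that.

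**Conclusion.** The point holds for the aim in Section 1.0. With zero contrasts between multifocal designs, the aim cannot be met at any sample size, and this needs no assumption. That the powered correlation ignores a constant error in the predicted mean effect is algebra, given one value per subject; the 87% figure only illustrates it and rests on assumed settings.

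Three further inferences are not supported:

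- A reader might conclude that N = 10 is wrong. It reproduces.
- A reader might conclude that measurement noise puts a correlation of 0.8 out of reach. The documents give no standard deviations from which to judge that, and it is a separate matter from the mismatch between aim and design.
- A reader might expect a model that gives every eye the same prediction to score a correlation of zero. The correlation would be undefined. Individual biometry, topography and lens centration are collected, so such a model does not appear to be intended.

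The study remains worthwhile as a first check of the model on one multifocal lens. What should change is the claim it may support and the way accuracy is reported.

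**What to change.** 1. In Section 1.0, in the aim that now reads "identify visual quality metrics that are correlated with changes in visual performance with different multifocal contact lens designs", replace the closing reference to several multifocal designs with: *between a single vision lens and one multifocal lens design*.
2. In the same section, add: *This pilot tests prediction for one multifocal lens. It will not support conclusions about comparing, ranking or screening other multifocal designs.*
3. Section 2.0 may stay, with the use for novel designs labelled as long-term rationale.
4. In Sections 8.0 and 20.0, add that the mean measured-minus-predicted change, multifocal against single vision, will be reported with limits of agreement alongside each correlation where model and measurement share a scale.

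**Cost.** The claim is narrower, and there is one small extra analysis of measurements already planned. No subjects, lenses or visits are added. The agreement estimates will be imprecise: with 10 subjects the 95% confidence interval for the mean difference is ± 2.262 / √10 = ± 0.72 of the SD of the differences. It should be reported with that interval and read as a pilot estimate.
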